Severity of outcomes, cost of care, and initiatives prioritizing access to CIH and whole health care warrant the need for a multi-dimensional approach, such as MR. The proposed research will advance science by: (1) testing a safe self-directed sustainable CIH approach for treating a clinically defined high-risk population of Veterans diagnosed with chronic pain and PTSD-related symptoms to improve psychological and physical outcomes; (2) introducing a non-pharmacologic chronic pain management program option for Veterans;

(3) testing the usefulness of MR as a remotely delivered internet/mobile program delivered in the users' natural environment; (4) leveraging a partnered approach (e.g., spouses or family members) to implementing interventions that address the biopsychosocial aspect of wellness; and (5) conducting longitudinal repeated-measures analyses, which are not common in CIH research.

Research Design and Methods

Study Design and Overview.

This four-year randomized controlled trial with one intervention arm and one wait-list control arm will utilize mixed methods to evaluate the effectiveness and perceived value of the MR program in relation to physical and psychological symptoms, global health, and social outcomes. An underpinning of the MR program is that it is intended to be adjunctive (complementary) to conventional evidence-based modalities for treatment of pain and PTSD (i.e. usual care). This is consistent with the previous MR trial conducted in a non-VA setting and different patient population whereby usual care served as the comparator group.

Therefore, a waitlist control condition has been selected as the comparator for the proposed trial. This will allow assessment of the MR program above and beyond the effects of usual care being received. In addition, the relatively brief waitlist control period insures that all subjects will ultimately be offered the MR program. We believe this will be an incentive for both recruitment and retention of study subjects for this new recruitment setting. We will test MR using a randomized control trial with concurrent mixed methods data collection. We will recruit Veteran and partner (e.g., spouse or family member) dyads. Study flow for each site is shown in Figure 2.

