Aim 1 & 2 assessment data will be collected from 600 Veteran/partner dyads (up to 200 per site, 100 dyads per arm) via a secure project website at baseline, 1, 2, and 4 months to assess primary and secondary outcomes. MR utilization and pain ratings will be assessed weekly for the first eight weeks of the intervention. This data collection plan will allow assessment of acute changes, rate of change with repeated measures over two months and sustained changes.

In **Aim 3**, a sub-sample of 84 individuals assigned to the intervention arm (n= 84 individuals, approximately 28 individuals/site) will be purposively selected (e.g., high or low MR utilization groups) to participate in telephone interviews to evaluate their experiences using the program. All consenting participants will be randomly assigned in a 1:1 ratio *using a permuted variable block design* to one of two arms (treatment vs. control). Participants will receive study information, instructions on how to complete the online data collection, and contact information in case they experience an adverse event. Participants will provide preferred contact information for data collection reminders. We will have contact information for each participant's primary care provider to ensure contact in the case of an adverse event and follow our established protocol for such events.

Treatment Arm: MR is a user-driven, dyadic, self-care management program developed with NIMH funding (R43/44) for use by Veterans and their selected partners, individually or together, to reduce pain and distress and support physical, mental, and relationship health. MR was designed for Veterans who face obstacles accessing formal mental health services. It can also be used to complement formal services. MR is a patient-centered intervention, allowing users to determine the pace at which to proceed in each program component.

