TBI Exposure	OHIO TBI Exposure Screen ⁶⁴	8-items designed to elicit self- or proxy-reports of TBI occurring over a person's lifetime. Can provide measures of the extent of exposure to TBI including the current injury.	5	Pre-screening
Veteran and Partner Independent Variables				
Demo-graphics	Participant Survey	15-items assess age, gender, ethnicity/race, education, income levels, religion, marital status, relationship length, military service/status/grade, deployments, computer/internet use.	5	Baseline
Veteran Independent Variable – Covariate				
Other Treatments	Concurrent treatments	2 items asking Veterans to report concurrent pain and PTSD treatment(s) and CIH modalities to account for dual intervention effects.	1	Baseline, months 1, 2, 4
Veteran Dependent Variables				
Quality of Life	Self-Assessment of Change ^{62,63}	16-item word pairing scale to assess a variety of shifts in well-being across a broad range of therapeutic modalities and conditions.	5	months 1, 2, 4

Quality of Life	Quality of Life SF12 ⁶⁵	12-items to assess quality of life using physical status and mental health distress.	3	Baseline, months 1, 2, 4
Pain	Defense and Veterans Pain Rating Scale ⁶⁶	10-point scale to measure “usual” pain intensity over the last week and 4 pain functionality (past month) items.	3	
	Pain Outcomes Questionnaire e- Short Form VA ⁶⁷	20-items assess pain-related domains, including pain intensity, interference with activities and mobility, negative affect, vitality, pain-related fear; and improbable pain-related symptoms.	5	
Pain	Single item scale	One item will assess pain using a 0 to 5-point Likert-type scale.	1	Baseline, weeks 1-8; months 1, 2, 4
Stress and Tension	Single item scales	Two items will assess stress and tension using a 0 to 5-point Likert-type scale.	1	
PTSD & Related Psychological Symptoms	PTSD: Posttraumatic Checklist ⁶⁸	20-item measure of the DSM-V PTSD symptoms with scales related to stress, anxiety, & emotional numbing.	4	Baseline, months 1, 2, 4
	Depression: Beck Depression Inventory ⁶⁹	21-items, a widely used instrument for measuring depression. Respondents are asked to rate their symptoms and attitudes using a 4-point scale.	5	
	Stress: Perceived Stress Scale ⁷⁰	10 Likert-scaled items, validated and widely used, to determine perceived stress levels.	3	

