	Sleep Quality: Pittsburgh Sleep Quality Index ⁷¹	19 self-rated questions from which 7 component scores are calculated and summed into a global score to assess sleep quality in the past month.	4	
Veterans and Partner Independent Variable - Covariate				
MR Program Utilization (Treatment and Control group)	Utilization survey	Treatment group: weekly report 11-items will assess frequency of use and compliance of the MR mind/body & massage practices. Control group: weekly report 4-items with descriptive activities to obtain descriptive data on their utilization of any personal strategies to address stress coping, physical pain, partner relationship support, and sleep quality.	3	weeks 1-8; months 1, 2, 4
Veterans and Partner Dependent Variables				
Relationship Satisfaction	Revised Dyadic Adjustment Scale ⁷² - Adapted	14-item Likert-scaled instrument is reliable and valid and contains subscales for dyadic consensus, dyadic satisfaction, and dyadic cohesion.	3	Baseline, months 1, 2, 4

Compassion	Compassion for Self and Others Scales ^{73,74}	26- (CSS) and 21- item (COS) measures, five-point Likert-scaled measures self-compassion and compassion for others.	5	
Program Satisfaction (Treatment Only)	MR Program Satisfaction Items	11 ten-point Likert-type items assess satisfaction using MR components, whether they would recommend MR, and massage satisfaction.	1	Weeks 1-8; months 1, 2, 4

(2) Telephone interviews.

To address **Aim 3**, telephone interviews (~30 min) will be conducted with a sub-sample of 84 individuals. Only treatment group members will be recruited for this data collection. Prospective interviewees will be purposively selected (e.g., high or low MR utilization groups) to participate in telephone interviews to evaluate their experiences using the program. MR utilization will be calculated at the dyadic level. Both Veteran and partner members of dyads assigned to the treatment arm will be contacted for qualitative interviews, however interviews will be conducted with Veterans and their partners separately. We will explain the interview purpose and ask permission to audio-record and use the interview script to ensure that all topics are covered. An audio voice consent must be completed and voice recorded at the time of the telephone interview process. The participant will be informed they will be recorded and need to state on the recorded telephone interview when asked if they agree to participate prior to the start of the telephone interview.

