The potential risks for participating in this study are minimal. No pharmacological therapies are used in this study. This study will be approved for adherence to Human Subjects Protection by the Institutional Review Board and R&D committees at both study sites. Subjects will be issued a coded identifier, which will be known only to the PI, project manager, and data manager; all records and the informed consent documents will be retained in locked files in the PI's or project manager's office. All computer data will be encrypted to protect patient confidentiality. HIPAA regulations will be strictly adhered to. Data will be secure on a networked computer system behind VA firewalls, and access will be restricted and password protected.

Participants will be assured that their participation is voluntary and they can choose not to answer any question. Participants will also be assured that they can choose not to participate in the study at any time. There is an intervention being offered in this study; there are no alternative options available for participants beyond standard of care treatment. The proposed study poses minimal risk to participants. As this intervention is palliative in nature with non-intrusive data collection, this is a minimal risk study. There is a risk that some patient participants may:

1. Feel uncomfortable reporting about their comorbid condition symptoms, specifically their PTSD;
2. Emotional and/or physical discomfort as a result of engaging in the MR activities
3. Experience agitation/distress during the intervention and/or data collection.

Unauthorized access to data is also a risk in all research studies. Based on our prior research, we believe that it is unlikely that these adverse events will occur, however we will implement several protective strategies to protect participants and their data. Should any behavioral or relationship issues arise during treatment, participants will have information to contact their providers and the research team for support. The research team will follow up directly with the Veterans' identified provider (at onset of participation) to ensure the Veteran has mental health support. All unanticipated incidents will be documented and reported in alignment with VA and Institutional Review Board regulations.

2. Adequacy of Protection from Risk

All study staff are up-to-date with VA Privacy and Information Security and Rules of Behavior training.

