Adverse or Serious adverse events: Any adverse event (AE) that: (1) results in illness or death; (2) is life-threatening (places the subject at immediate risk of death from the event as it occurred); (3) results in inpatient hospitalization or prolongation of existing hospitalization; (4) results in a persistent or significant disability/incapacity; (5) results in a congenital anomaly/birth defect; or (6) based upon appropriate medical judgment, may jeopardize the subject's health and may require medical or surgical intervention to prevent one of the other outcomes listed in this definition.

Since the study is utilizing a non-invasive palliative intervention and social-behavioral methods including surveys and telephone interviews, it is unlikely that recruiting participants in the described activities will cause an "adverse event" among the study population. However, it is possible that a Veteran participant and/or partner will become agitated or experience an adverse emotional/psychological response during the intervention and/or the data reporting process. In the event of an adverse event the project

manager and PI will follow regulated protocol. Then they will follow procedure to report the adverse event to the IRB. In anticipation of the unlikely event that a participant and/or partner might become agitated or distressed during the intervention or data collection period, each participant will be provided: (1) the PI's contact information; and (2) the national crisis hotline number for Veterans. The contact information of the Veteran's provider will be collected at onset of study participation for referral as appropriate (i.e., mental health), if indicated.

The participant may be formally excluded from further participation to ensure the individual's safety.

We are including an established process for responding to adverse events of suicide ideation. We provide resources for suicide ideation in all of the surveys that the participants take. Furthermore, when the participant responds affirmatively to the suicide ideation question in the online survey, they are immediately prompted to seek professional help through the VA crisis hotline. The VA crisis hotline provides 24 hour, 7 days a week free and confidential assistance with adverse events.

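### Apart from suicidal ideation, no survey item described asks about MR-related discomfort or distress, so a low adverse-event count cannot separate low risk from low capture, especially in partners

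*Combined protocol and SAP*

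**What the plan says.** **Risks named.** Potential Risks (Privacy and Information Security Information, 1.C) lists, for patient participants, "Emotional and/or physical discomfort as a result of engaging in the MR activities". The Adverse or Serious adverse events paragraph of the Data and Safety Monitoring Plan brings in the partner: "it is possible that a Veteran participant and/or partner will become agitated or experience an adverse emotional/psychological response during the intervention". The PTSD Specific Training and Protocol section also foresees partner distress.

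**What is asked.** In Table 1 the MR utilisation row reads "weekly report 11-items will assess frequency of use and compliance of the MR mind/body & massage practices". The control version has four items on personal coping strategies. The satisfaction items go to the MR arm only and cover satisfaction and recommendation. For Veterans, Table 1 adds single-item ratings ("One item will assess pain using a 0 to 5-point Likert-type scale"; "Two items will assess stress and tension using a 0 to 5-point Likert-type scale") at baseline, weeks 1 to 8 and months 1, 2 and 4. Veterans also complete the POQ, DVPRS, PCL, BDI and PSS at baseline and months 1, 2 and 4. Partners are listed only for demographics, utilisation, the RDAS, the compassion scales and, in the MR arm, satisfaction.

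**How events reach the log.** Participants receive "contact information in case they experience an adverse event" (Study Design and Overview). A suicidal-ideation question in the online survey triggers a crisis-line prompt and notice to the provider. Under Reporting, staff pass on events linked to carrying out the study, and the project manager keeps a log. The Updated Statistical Analysis Plan does not mention adverse events.

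**What is claimed.** Significance lists among the study's advances "testing a safe self-directed sustainable CIH approach for treating a clinically defined high-risk population of Veterans".

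**The concern.** The plan names specific risks and then, as far as the described instruments show, does not ask about them. With delivery and assessment both remote, a participant who is sore after a partner's massage or upset after a meditation exercise must volunteer the fact, or a staff member must notice it. Partners give and receive massage and practise the same techniques, yet Table 1 offers no score on which their distress would show.

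At stake is any safety statement drawn from the trial. The efficacy comparison is unaffected. But MR is described as safe and the Dissemination Plan foresees promotion within the VA, so a near-empty event log could easily be read as reassurance. Because staff report events judged to be connected with the study, a causal filter also operates before logging. Control-arm events may then be under-recorded, and event counts may not be comparable between arms.

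**Working it through.** The documents give no expected event rate, capture rate or safety precision, so there is no stated figure to reproduce. The check is a side-by-side reading, followed by an illustration.

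**1. Named risk against described measure**

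| Risk | Veteran | Partner |
|---|---|---|
| Physical discomfort from MR | Pain scores in both arms; no attribution to MR | No measure in Table 1 |
| Emotional discomfort, agitation | Stress, tension, PTSD and depression scores in both arms; no attribution | No symptom scale in Table 1 |
| Relationship problems | RDAS | RDAS |
| Suicidal ideation | Asked and escalated | Survey question described for participants generally |

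**2. A conflict to reconcile.** The Compensation section pays each participant for weekly pain ratings as well as utilisation reports. Table 1 lists the pain item for Veterans only. If partners do rate pain, the first partner cell changes; the second does not.

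**3. Illustration of what a zero or low count would mean.** Inputs from the documents: 600 dyads randomised 1:1, hence 300 MR Veterans and 300 MR partners; about 33% attrition, hence 300 × 0.67 = 201 per role. Assumption: capture probability s from 0.10 to 1.00. The roles are kept separate because members of a dyad are not independent.

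Exact 95% upper bound on the true rate after zero recorded events: (1 − 0.05^(1/n)) / s.

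| s | n = 300 | n = 201 |
|---|---|---|
| 1.00 | 1.0% | 1.5% |
| 0.50 | 2.0% | 3.0% |
| 0.25 | 4.0% | 5.9% |
| 0.10 | 9.9% | 14.8% |

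Now assume a true rate of 5%. The recorded count is binomial with n and 0.05 × s. The chance of three or fewer recorded events is:

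| s | n = 300: expected count | n = 300: chance of 3 or fewer | n = 201: chance of 3 or fewer |
|---|---|---|---|
| 1.00 | 15.0 | 0.02% | 0.9% |
| 0.50 | 7.5 | 5.7% | 26% |
| 0.25 | 3.75 | 48% | 76% |
| 0.10 | 1.5 | 93% | 98% |

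The same low count is strong evidence against a 5% rate under full capture and almost no evidence under poor capture. The spread comes entirely from s, which the documents do not give.

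**The case against.** The strongest reply is that harm is not invisible. Veterans in both arms repeatedly rate pain, stress, tension, PTSD and depression, and complete the Self-Assessment of Change at months 1, 2 and 4. Control dyads do the same assessments, so worsening can be compared by arm. Partners complete the RDAS and compassion scales in both arms. Staff must respond to distress that they see, the team monitors for events that lead to dropout, and MR-arm interviews ask about pros and cons. No aim concerns safety, and no planned test treats a low count as proof of it. Item-level survey text is not in the documents, so the absence of an item is inferred from one-line descriptions.

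Most of this stands, and it rules out stronger readings that a reader might infer:
- That symptoms go unasked, or that no arm comparison is possible: the Veteran scores contradict both.
- That partners are unobserved: their relationship and compassion scores are collected.
- That safety reporting is wholly passive: suicidal ideation is solicited, and staff observation adds a limited route.
- That a low count would show under-reporting, or that MR is unsafe: nothing in the documents supports either.

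What remains is that none of these routes links discomfort to MR or gives partners a symptom measure. The SAP plans no summary of individual worsening, and group means can improve while some people get worse. The interviews are confined to the MR arm. The attrition interviews number at most ten and leave out people who formally withdrew.

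**Conclusion.** The point holds as a cheap improvement to safety capture, not as a flaw in the efficacy analysis. Apart from suicidal ideation, the described surveys do not solicit MR-related discomfort or distress, Table 1 has no partner symptom scale, staff reporting is limited to study-connected events, and no analysis of adverse events or worsening is specified. A low event count therefore cannot by itself support safety, least of all for partners.

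Its size cannot be fixed from the documents. With zero events in 300 people per role, the upper bound runs from 1.0% to 9.9% as assumed capture falls from 100% to 10%. The conclusion rests on Table 1's descriptions reflecting the actual items, and on the unresolved conflict with the Compensation section about partner pain ratings.

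**What to change.** 1. Add one neutral item, with a short text field, to the utilisation survey: any new or worse physical discomfort, emotional upset or relationship problem since the last report. Both arms and both dyad members already complete that survey in weeks 1 to 8 and at months 1, 2 and 4. Follow a positive answer from an MR user with a question on whether an MR practice contributed.
2. Tabulate all responses by arm and by Veteran or partner. Have staff review, for the existing log, those attributed to MR or describing a significant event. Do not log every positive answer: 1,200 people asked 9 to 11 times give 10,800 to 13,200 responses, and much of what a chronic-pain sample reports will be background pain.
3. Add to the SAP a by-arm summary of Veteran worsening on the pain, stress, PTSD and depression scores already collected, with the definition of worsening fixed before the arms are compared. State which adverse events were solicited.
4. Reconcile Table 1 with the Compensation section on partner pain ratings.

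The cost is one or two short items in an existing online form, more minor reports to review, and possibly a less favourable event count. Repeated harm questions might also influence an unblinded self-reported pain outcome, so wording should be identical in both arms up to the attribution question.

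The SAP describes the qualitative work in the past tense, so survey collection may be over. If so, do step 3 only, state that events other than suicidal ideation were unsolicited, and make no claim about partner safety.

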Participants will not be paid for surveys that are not completed by the study end period (up to 4 months). These four time-points were selected to collect baseline for comparison, weekly to examine immediate effects, at 2-months to examine post intervention effects, and at 4-months to examine sustained intervention effects. The total possible incentive for participants is up to \$140.

4) Importance of Knowledge to be Gained

Advancing the science of implementing complementary and integrative health services into the VA system of care for Veterans and their partners is an important aspect of providing Veteran-centered care. VHA recognizes the need to develop a holistic approach to create a patient-centered experience for Veterans with comorbid conditions such as chronic pain and PTSD. This data will support the development of a Veteran-centric self-management intervention for Veterans and their partners (e.g. spouse, life partner) within the VA system of care.

5) Data and Safety Monitoring Plan

Risk of harm from this study is less than minimal risk. The principal investigator will be responsible for monitoring the safety and efficacy of the study, executing the data and safety monitoring plan and complying with the reporting requirements. The PI and project manager will provide a summary as part of the grant's progress report. The report will include participant's socio-demographic characteristics, expected versus actual recruitment rates, any quality assurance or regulatory issues that occurred during the past year, summary of adverse events, and any actions or changes with respect to the protocol. The research team will be trained in protecting the safety of the study participants and the scientific credibility of the project. We will also work with VA clinical psychologists, and Chief of PM&R [name], DO, to ensure our protocol is appropriate for Veterans with comorbid chronic pain and PTSD, as well as other conditions participants might have including substance abuse disorders and TBI. The team will coordinate to respond to any individual needs participants and their partners may present throughout the study.

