Additionally, a designated team member will contact the participant's current mental health provider, or, in the case they do not have a mental health provider, their primary care provider in a timely manner to report the incident and request immediate follow-up. The use of a local clinical psychologist will be unfeasible for this nation-wide participant population. Also, the decision to utilize the mental health or primary care provider that the Veteran has an established relationship with is ethical and Veteran-centric.

After participant's provider is notified, a designated study team member will follow up with the provider to ensure communication has occurred. In the case of participants who recurrently experience adverse events (e.g., responding to survey question with suicidal ideation if they 'had a chance') during the data collection period, study team members will continue to notify participant's provider until agreed upon by all parties (i.e., participant, provider, study team member) to desist on notifications.

If the participant does not have a designated mental health provider or primary care provider, we will escalate the issue to the local VA office's Suicide Prevention Team.

We have added language to the verbal informed consent, and also in the copy of the consent that is mailed to the study participants, that in the case of an AE or SAE, confidentiality may be breached by escalating the issue to the necessary health authorities, in order to protect the safety of the study participant and others.

Reporting: It is unlikely that any of the study procedures will cause an AE or SAE. Should an AE or SAE occur, study staff is trained to immediately report AEs connected to implementation of the study to the project manager, and Drs. [name] (PI), [name] (Site PI), and [name] (Site PI). They will also be escalated, in the case of suicide ideation, to the mental health provider or primary health care provider. The study project manager will keep a log of AEs and SAEs. In the event of an SAE, we will file a report with VA Tampa R&D

and the IRB. As part of this process the IRB will determine if the event is directly related to project procedures, so that it can be determined if project procedures should be modified. Information about all AEs and SAEs will be provided in annual progress reports.

6) Inclusion of Women, Minorities, and/or Children

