Different correlation structures and functional forms of the effects of the MR program will be assessed using the information criteria and a final parsimonious model will be determined for final statistical inference. For H1.1, the primary outcome measure for pain will be the total score on the 19-item POQ, and its subscales. Additional analyses will be performed on the DVPRS, and the weekly 5-point Likert-scale Pain item. For H1.2, the primary outcome measure for PTSD will be total score on the 20-item PCL-5. For H1.2, the outcome measure for psychological symptoms is PSS; the outcome measure of sleep is PSQI; and the outcome measure for QOL is the SF12 and BDI. For H2.1, the outcome measure for relationship satisfaction is the RDAS. Additional analyses will be performed on the COS and CSS measures, the weekly 5-point Likert-scale Stress item, and the weekly 5-point Likert-scale Tension item.

Qualitative data analysis followed Inductive and deductive coding methods. A qualitative code book, consisting of known constructs from the literature and those that emerged inductively from the data, was created. Two trained qualitative researchers coded the data using the qualitative analysis software program, ATLAS.ti v. 22. To establish intercoder reliability at 80%, two qualitative researchers coded 20% of the interviews (initially every 5th transcript then randomly to ensure coding consistency) separately then compared codes to determine percent of agreement. Coded text in ATLAS.ti v. 22 was exported and further analyzed in Excel spreadsheets to develop themes. To enhance credibility, initial findings were presented during quarterly stakeholder meetings to provide input and facilitate refinement of findings.

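### Suicidal-ideation answers are collected in both arms and handled as adverse events, but nothing in the plan requires them, or AEs and SAEs generally, to be tabulated by randomised arm

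*Combined protocol and SAP*

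**What the plan says.** The Data and Safety Monitoring Plan (item 5, adverse events) states: "We are including an established process for responding to adverse events of suicide ideation". The process starts "when the participant responds affirmatively to the suicide ideation question in the online survey": the participant is pointed to the crisis line and the participant's provider is notified. The same section covers "participants who recurrently experience adverse events (e.g., responding to survey question with suicidal ideation", so a survey answer is itself the protocol's example of an adverse event.

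Aggregate reporting is described in two places. The progress report is to include a "summary of adverse events, and any actions or changes with respect to the protocol". The Reporting paragraph adds: "Information about all AEs and SAEs will be provided in annual progress reports". Neither sentence mentions arm, timing relative to baseline, or participants versus events. The project manager keeps a log, and staff are trained to report events connected to carrying out the study.

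The Data Analysis section and the Updated Statistical Analysis Plan list patient-reported outcomes fitted with GROUP, TIME and GROUP x TIME terms. The depression scale is among them ("the outcome measure for QOL is the SF12 and BDI"), as are the PCL-5 and the Perceived Stress Scale. No adverse-event table, ideation endpoint or safety comparison appears. The Missing data paragraph does plan a tabulation by arm and wave, but of missingness only.

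**The concern.** Ideation can be expected in Veterans with PTSD and chronic pain whether or not they use MR. A single case, or a case-by-case judgement of relatedness, therefore cannot show whether MR raises or lowers its frequency; a comparison of randomised arms can. The data for that comparison will exist, since the Usual Care Waitlist Control Arm section has control dyads complete all the assessments, and the Sampling section reveals group assignment only once baseline collection is complete.

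The Significance section describes the work as "testing a safe self-directed sustainable CIH approach for treating a clinically defined high-risk population of Veterans", and Potential Risks names emotional discomfort, agitation and distress. The abstract says the evaluation is needed to judge whether MR is appropriate for use within the VA. If the plan is followed to the letter, the trial can finish without any by-arm statement on the most serious form of distress it asks about.

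**Working it through.** **1. Reading the sections together.** No arithmetic is needed for the core point.

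| Question | Where | Finding |
|---|---|---|
| Is ideation asked about and treated as an AE? | Data and Safety Monitoring Plan | Yes |
| Do both arms complete the same assessments? | Usual Care Waitlist Control Arm | Yes |
| Are baseline answers pre-exposure? | Sampling | Yes; assignment follows baseline |
| Is an aggregate AE report planned? | Data and Safety Monitoring Plan | Yes; format not stated |
| Is any AE or ideation count by arm planned? | Data Analysis; Updated SAP | No |
| Would the AE log serve as the source? | Reporting paragraph | Doubtful; staff reporting is limited to events connected to the study |

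**2. What the existing models show.** A linear mixed model on a depression, PTSD or stress total estimates a difference in means or slopes. It can detect average worsening, but it does not give the number or proportion of people with an affirmative ideation answer.

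**3. How informative would a by-arm table be?** The plan states no figure to reproduce. Two sample sizes bracket the answer for Veterans:

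- From the recruitment target: 600 dyads at 1:1 gives 300 Veterans per arm; less 33% attrition, 300 x 0.67 = 201.
- From the power statement (d = 0.38, 80% power, two-sided 0.05), on a plain two-sample reading: n = 2(1.96 + 0.842)^2 / 0.38^2 = 15.70 / 0.1444 = 108.7, so 109 per arm.

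These do not agree (201 per arm would give a detectable d of 2.80 x sqrt(2/201) = 0.28), so both are carried as a range.

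The documents give no ideation rate. The waitlist risk p is an assumption, and the MR risk is set at 2p. Arcsine approximation: h = 2 asin(sqrt(2p)) - 2 asin(sqrt(p)); power = Phi(h x sqrt(n/2) - 1.96).

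| Assumed risk, waitlist to MR | h | Power, n = 109 | Power, n = 201 |
|---|---|---|---|
| 1% to 2% | 0.084 | 9% | 13% |
| 2% to 4% | 0.119 | 14% | 22% |
| 5% to 10% | 0.193 | 29% | 49% |
| 10% to 20% | 0.284 | 55% | 81% |
| 15% to 30% | 0.364 | 77% | 95% |

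Half-width of the 95% interval for the risk difference when both arms have risk p, 1.96 x sqrt(2p(1-p)/n), for p = 5%, 10% and 15%: 5.8, 8.0 and 9.5 percentage points at 109 per arm; 4.3, 5.9 and 7.0 at 201.

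**The case against.** Several objections have force.

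- **Silence is not a prescription.** A reader might infer that the plan mandates a pooled total that hides any excess under MR. The reporting sentences give no format, and a by-arm summary would be compatible with them. What stands is that nothing requires one.
- **The make-up of the log is unknown.** A reader might try to work out what share of logged events would come from baseline, waitlist and MR answers. Because staff reporting is limited to study-connected events, the documents do not show which answers are logged, so no such split can be supported.
- **Distress is already compared by arm.** Depression, PTSD and stress scores are all modelled by group, and those models can show harm as well as benefit. It would be wrong to say that they could register only a trivial shift: that supposes ideation rises while every other depression item stays flat. Nor do the documents say that the ideation question is a depression-scale item. The narrower point stands: mean scores do not count people with ideation.
- **Scope.** The abstract's Impact paragraph leaves suicide risk to possible later evaluation, and no hypothesis claims safety. That explains why ideation is not an efficacy endpoint. It does not explain leaving recorded adverse events without a by-arm table.
- **Rarity.** If ideation is rare, the table will say little and could be misread as reassurance. This is correct and governs how it must be labelled.

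**Conclusion.** The point holds as an omission in the analysis and reporting plan: harm data collected in both randomised arms have no required by-arm tabulation. Efficacy inference is untouched, and this is a modest, worthwhile reporting improvement. The documents do not support the stronger conclusion that an excess under MR would necessarily go unreported, nor is this a criticism of how individual participants are protected.

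The core rests on the text alone. The precision figures rest on assumed risks and on 109 to 201 Veterans per arm: power for a doubling of 29% to 95% at waitlist risks of 5% to 15%, and 9% to 22% at 1% to 2%. An interval that includes zero would therefore not be evidence of no difference.

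**What to change.** Add a descriptive safety paragraph to the Updated Statistical Analysis Plan:

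1. **Source.** Use the stored survey answers, not the AE log, which may be filtered by judged relatedness.
2. **Measure.** By randomised arm, and separately for Veterans and for partners (if partners are asked the question), give the number and proportion with any affirmative ideation answer after baseline, counting each participant once. Show baseline answers separately as pre-exposure, and identify answers that are new since baseline.
3. **Denominator.** Randomised participants with at least one post-baseline survey containing the question. State which surveys contain it, and report completion by arm and wave.
4. **Missing surveys.** Add a sensitivity analysis, for example with the multiple imputation already planned. Missingness may depend on the outcome, since a distressed participant may be excluded from further participation.
5. **Estimate.** Risk difference with 95% CI, adjusted for the baseline answer where counts allow.
6. **AEs and SAEs.** List post-baseline events by arm, as participants and as events.
7. **Label.** Descriptive; not a test of no difference.

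The cost is one SAP paragraph and one or two tables, with no new data, visits or staff. The drawback is imprecision if ideation is rare. No change to the response procedures is proposed.
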